## Précis

Calcinosis, a serious complication of dermatomyositis, involves deposition of calcium (carbonate apatite) in soft tissue, and can result in negative impacts on quality of life and physical function. To date, there are no known effective therapies that are approved for the treatment of dermatomyositis-associated calcinosis, and there is no consensus within the medical community on the optimum treatment strategy for this often-debilitating condition.

A few reports in the literature describe treatment successes with a variety of therapeutics; however, these data are from anecdotal reports or case series and thus provide limited scientific evidence of effectiveness. Recently published reports as well as personal observations within our group have suggested that intravenous sodium thiosulfate treatment may benefit calcinosis patients. In order to gather more robust data on the utility of this medication in the treatment of calcinosis associated with adult and juvenile dermatomyositis, we propose to evaluate its effects in the context of a prospective clinical trial.

We plan to enroll participants at a single center into a single-arm, open-label study, with the overall objective of evaluating the efficacy and safety of intravenous sodium thiosulfate use in patients with moderate to severe extensive calcinosis associated with juvenile and adult dermatomyositis.

The study will enroll a maximum of 18 participants over 4 years into the full study, but up to 250 patients may screen for study entry. Eligible patients will be age 7 or older, and will have extensive calcinosis (defined as calcinosis involving the torso or 2 extremities) and moderate to severe calcinosis (indicated by a calcinosis activity visual analogue scale score of greater than or equal to 3.5 cm out of 10 cm).

Two separate evaluations performed at the NIH prior to initiation of therapy will be used as baseline data to compare in a pairwise manner to the change in assessments following treatment with sodium thiosulfate, with all other medications remaining stable. Study treatment will be 16 g/m^2 sodium thiosulfate administered 3 times weekly over a period of 10 weeks at the NIH. Subjects who complete 10 weeks of treatment or reach the primary end point by week 6 will be considered completers. Following the treatment period, all participants will return to the NIH for evaluations at weeks 24 and 62.

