## 2.1. Outcome Measures

- The primary outcome measure of the study will be greater improvement in calcinosis activity VAS rating from Week 0 to Week 10, compared with any change in calcinosis activity VAS rating observed during the pre-treatment period (from Week -10 to Week 0).

Secondary outcome measures include:

- Greater improvement in quality of life score (CHQ-PF50 for children, SF-36 for adults) from Week 0 to Week 10, compared with any change in quality of life score observed during the pre-treatment period (from Week -10 to Week 0).
- Changes in components of quality of life over time, as measured by quality of life questionnaires (e.g., SF-36, CHQ-PF50, PROMIS, Skindex-29)
- Changes in functional disability over time, measured by CHAQ/HAQ, CMAS/AMAT/Myositis Functional Index, and physical therapy-related assessments (e.g., range of motion, 6-minute walk, timed up and go, sit to stand, Motor Functional Measure (MFM))
- Change in muscle strength over time, measured by manual and quantitative muscle testing

**Abbreviated Title:** Sodium Thiosulfate (STIC)

**Version Date:** July 07, 2023

- Improvement of calcinosis lesions, assessed by Calcinosis Assessment Tool, Sentinel Calcinosis Lesion form, Mawdsley Calcinosis Questionnaire, durometry measurements, photography, and imaging studies
- Changes in gene expression, measured by RNA and protein analyses (e.g., to evaluate changes due to therapy, or differences between responders and non-responders to therapy)
- Incidence and severity of adverse events, including laboratory abnormalities, over time
- Improvement in or stabilization of myositis activity and damage, as assessed by the IMACS core set measures

Secondary outcomes will evaluate for differences in change from week -10 to 0 compared to week 0 to 10 as well as changes at week 24 and 62.

An additional outcome will be validation of the Calcinosis Assessment Tool and the Mawdsley Calcinosis Questionnaire and new imaging modalities for calcinosis, which are under development by our group and associate investigators of the protocol.

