- **Week 62:** At approximately 62 weeks following the Week 0 visit, participants will return to the NIH for a final evaluation and study completion. The study visit is expected to take up to 3-5 days and may be done as an inpatient or outpatient, depending on the needs and mobility of the participant. For participants who are unable to physically return to the NIH, the study team will attempt to complete as many of the assessments as possible by telehealth, phone, e-mail, and mail.

**Abbreviated Title:** Sodium Thiosulfate (STIC)

**Version Date:** July 07, 2023

[figure not shown]
- **Reminder Contacts:** Approximately 1 week and 6 weeks (as relevant; e.g., for Week 24 and Week 62 visits) prior to each study visit, participants may receive reminder contacts (e.g., phone, text, or email) with information about the date and time of future scheduled visits and, if applicable, any instructions necessary to prepare the participant for the visit. Additional reminders may be made as needed.
- **Early Withdrawal Due to Rapid Response:** Patients may be deemed completers at week 6 if they have scored a moderate improvement on the physician assessment of change and are believed to have reached maximal benefit as evidenced by a calcinosis VAS score of less than or equal to 10 mm. They will receive the week 6 assessments and then will not complete any of the infusions or assessments for the study for week 7-9. They then will return at week 10 for those evaluations, without receiving any sodium thiosulfate infusions that week, and will go on to receive the normal week 24 and 62 assessments.
- **Early Withdrawal Due to SAE:** Patients who experience a SAE where it is felt it is unsafe for them to continue to receive study drug will continue to be assessed according to the protocol schedule. Those assessments thought to be of increased risk due to their SAE will not be performed. For patients who are limited in their ability to follow up, the focus will be on assessments at week 6, 10, 24, and 62.

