## **8. Study Statistical Considerations and Analytic Plan**

### **8.1. Statistical Analyses**

A single-arm, open-label study is proposed to evaluate the primary hypothesis that participants treated with sodium thiosulfate will experience greater improvement in calcinosis activity as assessed by a change in the calcinosis visual analogue scale (VAS) after treatment compared with any change in calcinosis activity visual analogue scale during the observation period prior to treatment with sodium thiosulfate.

A intention-to-treat statistical analysis will be performed where first, the primary outcome, the change in calcinosis activity VAS score from Week 0 to Week 10 compared with any change in calcinosis activity VAS score observed during the pre-treatment period (from Week -10 to Week 0), will be analyzed using a two-tailed paired t-test. This will be reported as absolute change for the primary outcome and calculated by taking value of the time 0 score minus the time -10 score and subtracting from that the value of the time

**Abbreviated Title:** Sodium Thiosulfate (STIC)

**Version Date:** July 07, 2023

10 score minus the time 0 score. As secondary end points, we will also evaluate any changes as relative percent change and absolute percent change. Second, two-tailed paired t-tests will be performed to test for significant differences in the primary outcome for the adult and juvenile dermatomyositis patients separately. Multiple testing adjustments will be used to control for the multiple comparisons on the VAS score outcomes for the subgroup analysis.

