The validity of the calcinosis assessment tool (CAT) will be assessed by focusing on the similarity between the CAT and other disease activity measures, like the Global Physician Score (GPhS) and Patient Reported Outcomes Measurement Information System (PROMIS®). Large disagreement between the CAT and other disease activity measures would suggest that the CAT tool is not measuring improvement in calcinosis but small differences may indicate that the CAT is capturing improvement in calcinosis that the other measures are not capturing. To assess the similarity between the disease activity measures, the Spearman rank correlation coefficient between the change in the CAT responses and the change in the other disease activity measure responses will be calculated. One can then test whether this correlation coefficient is different than zero, which would suggest an association between the two measures. A kappa statistic will be calculated to assess the agreement between discrete measures in the CAT and other discrete measures of disease activity. In the case where the number of categories observed by the CAT and other discrete measures of numbers of categories differ, the comparison will be accomplished by comparing the pooled scores for all categories of

**Abbreviated Title:** Sodium Thiosulfate (STIC)

**Version Date:** July 07, 2023

the CAT to the pooled scores of each independent finding using a nonparametric Wilcoxon ranked sum statistic. Evaluation of the Mawdsley Calcinosis Questionnaire will be performed in the same manner as for the CAT. A cluster analysis will be considered to explore how well the change in VAS, along with other measures of disease activity, such as change in Global Physician Score, Patient Reported Outcomes Measurement Information System, MRI, CT scans, DEXA scans and vascular imaging, can distinguish between responders to intravenous sodium thiosulfate therapy and non-responders. Responders will be defined as those individuals who meet the primary end point and non-responders will be those individuals who fail to meet the primary end point. A Spearman rank correlation coefficient will be used to identify disease activity measures that are highly correlated and contain the duplicate information. This will aid in variable selection for future multivariate analyses to identify responders to therapy. We will also attempt to assess the responsiveness of these tools through their standardized response means.

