## 8.2. Sample Size Considerations

Sample size estimates for this analysis are based on the following assumptions:

1. The primary outcome is the mean difference in the change in calcinosis activity during the pre-treatment period and the change in calcinosis activity during the treatment period.
2. The calcinosis activity will be measured by the calcinosis visual analogue scale (VAS) score. This score ranges from 0 to 100 mm.
3. Pre-treatment period change in calcinosis activity is calculated by subtracting the calcinosis VAS score at Week -10 from the calcinosis VAS score at Week 0. Treatment period change in calcinosis activity is calculated by subtracting the calcinosis VAS score at Week 0 from the calcinosis VAS score at Week 10.
4. The treatment period change in calcinosis activity subtracted from the pre-treatment period change in calcinosis activity is approximately normally distributed or can be transformed such that it will be approximately normally distributed.
5. The sample size estimate is the sample size required after attrition.

There are few prior data on the use of sodium thiosulfate for treatment of the calcinosis comorbidity in dermatomyositis patients. Therefore, there is limited information to estimate the necessary sample size to achieve adequate power. For the power analysis, a standard deviation ranging between 5 and 20 mm is assumed for the difference in the change in calcinosis activity between the treatment and pre-treatment periods based on previous studies that use visual analog scale measurements (Kelly 2001 and Demoly et al. 2013). The power analysis is based on two-sided, paired t-tests with a within subject correlation of 0.5 and 90% power. The sample sizes required for a range of significance levels, assumed standard deviations, and mean differences in the change in calcinosis activity VAS score between the pre-treatment and treatment period are given in Table 3.

**Table 3 Sample Sizes required, after attrition, to detect significant differences in the change in calcinosis activity between the pre-treatment and treatment periods. The estimates are based on two-sided, paired t-tests and 90% power where  $\alpha$**

**Abbreviated Title:** Sodium Thiosulfate (STIC)

**Version Date:** July 07, 2023

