### 8.3. Accrual Number

Based on the information provided in preliminary data, unpublished reports, other studies involving sodium thiosulfate therapy, and the power analysis, the targeted number of participants to complete this study is 13. Considering the involved schedule of this therapy balanced with the lack of alternative treatment options for these patients, we anticipate a dropout rate of approximately 25%. Thus, to achieve a final sample size of 13 participants completing the study, we plan to enroll 18 participants. As discussed initially completers will be patients who receive all infusions or who reach the primary end point by week 6. For patients who need medication escalation prior to week 10 we will attempt to enroll another patient to use for the primary analysis instead of them as long as the total enrollment is still 18 or less patients.

Based on our experience enrolling a similar population, we anticipate screening approximately 5-6 individuals for every 1 eligible participant. Thus, we anticipate screening approximately 100 individuals for this study. Screening will be done by phone or in person interview and review of medical records. If the patient has been involved in other research studies information from those studies may also be considered.

**Abbreviated Title:** Sodium Thiosulfate (STIC)

**Version Date:** July 07, 2023

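### Responders are defined from VAS change and then used to judge how well VAS change identifies responders; no individual criterion is stated, and the completer wording disagrees between sections

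*Combined protocol and SAP*

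**What the plan says.** **Responders.** Section 8.1 states: "Responders will be defined as those individuals who meet the primary end point"; everyone else is a non-responder. The split feeds Fisher exact tests and an exploratory cluster analysis (both Section 8.1). Section 2.1 also mentions responder versus non-responder differences in gene expression. The cluster analysis asks how well change in VAS, together with the global physician score, PROMIS, MRI, CT, DEXA and vascular imaging, tells the two groups apart.

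**The primary end point.** Section 2.1 describes it as "greater improvement in calcinosis activity VAS rating from Week 0 to Week 10", set against the change from Week -10 to Week 0. Section 8.2 states: "The primary outcome is the mean difference in the change in calcinosis activity during the pre-treatment period" and during the treatment period. Section 8.1 gives the calculation: "taking value of the time 0 score minus the time -10 score and subtracting from that the value of the time", and the sentence continues with the Week 10 minus Week 0 change. Section 3.4 places the primary end point assessment at Week 10. None of these names a value that an individual must reach.

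**Completers.** The Précis says: "Subjects who complete 10 weeks of treatment or reach the primary end point by week 6 will be considered completers". Section 8.3 says: "As discussed initially completers will be patients who receive all infusions or who reach the primary end point by week 6". Section 3.1 (early withdrawal due to rapid response) uses another week 6 rule: physician-rated moderate improvement and maximal benefit, "as evidenced by a calcinosis VAS score of less than or equal to 10 mm". Section 5.5 adds that a patient found pregnant before week 10 is not a completer for evaluating the primary outcome.

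**The concern.** Sections 2 and 3.3 say that no validated measure of calcinosis exists and that the trial should show which tools are useful. A comparison of tools against responder status is informative only if that status is not derived from one of the tools. Here it is derived from calcinosis VAS change, so VAS must look good whatever the merits of CT, DEXA or PROMIS.

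The missing criterion makes this worse. Whoever analyses an open-label trial with a physician-rated outcome can choose who counts as a responder after seeing the data, and the group sizes swing widely with that choice.

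The completer wording raises a separate issue. The trial aims for 13 completers, yet its sections do not agree on who is one, and the week 6 route in two of them refers to an end point that does not exist at week 6.

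**Working it through.** **1. The plan's own figure.** Inputs from Section 8.2: two-sided paired t-test, significance level 0.05, SD of the difference 10 mm, mean difference 10 mm. Exact power from the noncentral t distribution is 91.1% with n = 13 and 88.3% with n = 12, so 13 is reproduced. With 25% dropout (Section 8.3), 13 / 0.75 = 17.3, rounded up to 18. No responder rate enters this calculation.

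**2. The individual quantity.** From Section 8.1, for each patient

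D = (V0 − V−10) − (V10 − V0).

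Lower VAS is better, so D > 0 favours treatment. D can be computed for every patient; only the cut-off is missing.

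**3. Circularity.** Let A = V0 − V−10 and B = V10 − V0, with equal variances and correlation r. Then D = A − B, and the correlation between D and the treatment-period improvement −B is

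(1 − r) / √(2 − 2r).

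| r | correlation of D with treatment-period VAS improvement |
|---|---|
| −0.5 | 0.87 |
| 0 | 0.71 |
| 0.5 | 0.50 |

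These correlations arise from the algebra alone, with no drug effect. If change in VAS means D itself, any cut-off on D separates the groups perfectly. CT, DEXA, MRI and PROMIS have no such built-in link.

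**4. Size of the responder group under the sign reading.** P(D > 0) = 1 − Φ(−μ/σ), with D approximately normal (Section 8.2).

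- No effect, μ = 0: 50% at every SD from 5 to 20 mm, or 0.5 × 13 = 6.5 of 13.
- Design effect, μ = 10 and σ = 10: 1 − Φ(−1) = 84%, or 0.84 × 13 ≈ 11 of 13. With μ = 10, SDs of 5, 15 and 20 mm give 98%, 75% and 69%.
- No effect, but also requiring V10 < V0: with c the correlation in the table, 0.25 + arcsin(c)/(2π) gives 42%, 37.5% and 33% for r = −0.5, 0 and 0.5.
- No effect, with regression to the mean after selection at the 35 mm entry minimum: simulation gives 41% to 49% (assumed VAS mean 35 to 55 mm, SD 15 mm, between-visit correlation 0.5 to 0.8).

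At 11 responders and 2 non-responders, a Fisher test on a yes/no feature is nearly uninformative. If both non-responders have the feature and 0, 1 or 2 responders share it, p = 1/78 = 0.013, 11/286 = 0.038 and 55/715 = 0.077.

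**5. Completer wording side by side.**

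| Place | Main route | Week 6 route |
|---|---|---|
| Précis | 10 weeks of treatment | primary end point by week 6 |
| Section 8.3 | all infusions | primary end point by week 6 |
| Section 3.1 | not stated | physician-rated moderate improvement, and VAS of 10 mm or less |

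D needs V10, so it does not exist at week 6. Putting V6 in its place would set a six-week change against a ten-week one. Nor is the Section 3.1 rule the same criterion. A patient at the 35 mm entry minimum must fall 25 mm (25/35 = 71%) to reach 10 mm. If the single change had mean fall 10 mm and SD 10 mm (assumed), 1 − Φ(1.5) = 7% would do so, against 84% for a fall of any size. For assumed mean falls of 10 to 20 mm and SDs of 10 to 15 mm, the ranges are 7% to 37% against 75% to 98%.

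**The case against.** The strongest reply is that the damage is confined. The primary analysis is labelled intention-to-treat, the cluster analysis is only to be considered, and the correlations serve variable selection for later work. D can be computed per patient, so the end point is not purely a group mean. Section 3.1 gives a workable week 6 rule, Table 4 schedules a rapid-responder check, and Section 8.3 explicitly refers back to an earlier description. On that reading the Précis and Section 8.3 are loosely worded and Section 3.1 governs.

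Much of this stands. What is missing is a cut-off, not an individual quantity, and the consequences are secondary. But none of it removes the circularity, which no choice of cut-off would cure. Nor does any section say that Section 3.1 defines the week 6 route elsewhere, and the difference between 10 weeks of treatment and all infusions remains.

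Four stronger inferences are tempting and unsupported:

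- *Half of untreated patients will be called responders.* There is no untreated arm, and 50% needs zero effect, symmetry about zero, and any D > 0 counting.
- *The power rests on these definitions.* The primary t-test and the calculation of 13 do not use the responder definition. Withdrawn patients are still to be assessed where possible (Sections 3.1 and 14.2), and replacement is triggered by medication escalation (Sections 4.1 and 8.3).
- *An all-infusions rule would leave too few completers.* The documents give no rate of missed infusions, so no shortfall can be calculated.
- *The planned 10 mm is the natural cut-off.* It is a detectable group mean. The documents do not support it as a threshold for one patient.

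**Conclusion.** The concern holds in a limited form. Judging VAS change against a responder status built from VAS change is wrong as written, and it biases the comparison of measures in favour of VAS. The individual criterion is unstated. Under the sign reading, the responder share runs from about 50% with no effect (33% to 49% under the other readings and assumptions shown) to about 84% at the design effect with SD 10 mm.

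The completer wording is inconsistent on two counts: a Week 10 end point to be reached by week 6, alongside a different rule in Section 3.1; and 10 weeks of treatment against all infusions. It matters because enrolment targets 13 completers and Section 5.5 ties completer status to evaluation of the primary outcome. The responder percentages rest on normality and the stated SD range; the week 6 percentages also rest on assumed means and SDs for a single change. The consequence falls on the responder analyses and on the count of completers.

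**What to change.** 1. In Section 8.1, remove calcinosis VAS change from the variables used to separate responders from non-responders, or report it only as a descriptive check outside the comparison with the other measures.
2. Before analysis, state the individual responder criterion as a value of D from Section 8.1, chosen and justified by the sponsor, and use it for the Fisher tests, the gene-expression contrast and the cluster analysis alike.
3. Reconcile the completer wording in the Précis and Sections 3.1, 5.5 and 8.3 into one definition that can be evaluated when it is applied, including at week 6. Which rule applies is for the sponsor.

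The cost is wording in the protocol and analysis plan; no new data are needed. The downside is that VAS change is no longer ranked among the discriminators in an exploratory analysis.

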## 8.2. Sample Size Considerations

Sample size estimates for this analysis are based on the following assumptions:

1. The primary outcome is the mean difference in the change in calcinosis activity during the pre-treatment period and the change in calcinosis activity during the treatment period.
2. The calcinosis activity will be measured by the calcinosis visual analogue scale (VAS) score. This score ranges from 0 to 100 mm.
3. Pre-treatment period change in calcinosis activity is calculated by subtracting the calcinosis VAS score at Week -10 from the calcinosis VAS score at Week 0. Treatment period change in calcinosis activity is calculated by subtracting the calcinosis VAS score at Week 0 from the calcinosis VAS score at Week 10.
4. The treatment period change in calcinosis activity subtracted from the pre-treatment period change in calcinosis activity is approximately normally distributed or can be transformed such that it will be approximately normally distributed.
5. The sample size estimate is the sample size required after attrition.

There are few prior data on the use of sodium thiosulfate for treatment of the calcinosis comorbidity in dermatomyositis patients. Therefore, there is limited information to estimate the necessary sample size to achieve adequate power. For the power analysis, a standard deviation ranging between 5 and 20 mm is assumed for the difference in the change in calcinosis activity between the treatment and pre-treatment periods based on previous studies that use visual analog scale measurements (Kelly 2001 and Demoly et al. 2013). The power analysis is based on two-sided, paired t-tests with a within subject correlation of 0.5 and 90% power. The sample sizes required for a range of significance levels, assumed standard deviations, and mean differences in the change in calcinosis activity VAS score between the pre-treatment and treatment period are given in Table 3.

**Table 3 Sample Sizes required, after attrition, to detect significant differences in the change in calcinosis activity between the pre-treatment and treatment periods. The estimates are based on two-sided, paired t-tests and 90% power where  $\alpha$**

**Abbreviated Title:** Sodium Thiosulfate (STIC)

**Version Date:** July 07, 2023

